4.8.2.2 Vital Signs

Descriptive statistics for vital signs [blood pressure (systolic and diastolic), pulse, respiratory rate, temperature, height (or length depending on age), body weight (using a certified weight scale), and BMI] and their changes from baseline at each post-baseline visit will be presented. The change to last visit will also be summarized. Shift tables for the number of patients with changes from baseline to highest and lowest post-baseline value based on the normal ranges as outline in [Appendix 7](#) will be provided.

If height is collected as length, it will be converted as following:

$$\text{Height (cm)} = \text{length (cm)} - 0.7 \text{ cm.}$$

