	-56 to -21	-49 to -14									
Study Days	Clinic Visit 1	Clinic Visit 2	1	14 ± 3	28 ± 3	56 ± 3	84 ± 3	112 ± 3	140 ± 3	168 ± 3	196 ± 7
Clinic Visits			Clinic Visit 3	n/a	Clinic Visit 4	Clinic Visit 5	Clinic Visit 6	Clinic Visit 7	Clinic Visit 8	Clinic Visit 9	Clinic Visit 10
Phone Call				X							
Patient/Caregiver/ Clinician Global Impression of Symptoms			X		X		X			X	
Clinician assessment of xanthoma			X				X			X	
Pregnancy test m	X serum	X urine	X urine		X urine	X urine	X urine	X urine	X urine	X urine	X urine
Study drug dispensed n			X		X	X	X	X	X	X	
Adverse events o	All Adverse Events										
FSV Deficiency Questionnaire	X	X	X	X	X	X	X	X	X	X	X
Study drug compliance				X	X	X	X	X	X	X	X
eDiary compliance i		X	X	X	X	X	X	X	X	X	X
Exit Interview										X	

AFP: alpha-fetoprotein; eCRF: electronic case report form; eDiary: electronic diary; EOT: end of treatment; FSV: fat soluble vitamin; ICF: informed consent form; INR: international normalized ratio; p-C4: plasma 7α hydroxy 4-cholesten-3-one; PedsQL: Pediatric Quality of Life Inventory; PK: Pharmacokinetic; QoL: quality of life; SAE: serious adverse event.

a All assessments will be performed before dosing unless otherwise noted.

b The two screening visits must be separated by at least 7 days, and Screening Visit 2 must occur at least 14 days prior to Study Day 1.

c An EOT visit must be performed as soon as possible if study drug is prematurely discontinued. The EOT visit requires the same assessments as the Week 24 visit.

d The Safety Follow-up visit is required 28 days (±7) following the Week 24/EOT visit or the date of last dose for patients who prematurely discontinued study treatment. See Section 7.1.3 and Section 7.1.4 for when a Safety Follow-up visit is not required.

- e The ICF (and assent) must be signed before any study procedures are performed.
- f Past (within 28 days prior to Screening Visit 1) and current medication will be documented in the eCRF.
- g A full physical exam including skin exam will occur at Screening Visit 1 and Day 1. At all other clinic visits a skin exam and symptom-based physical exam will occur. Findings from the symptom-based physical exam will be documented as adverse events if appropriate.
- h Includes blood pressure, pulse, respiratory rate, temperature, height (or length depending on age), and body weight.

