#### **10.2.7 Vital Signs**

Evaluation of vital signs will be performed at all clinic visits. This includes blood pressure (systolic and diastolic), pulse, respiratory rate, temperature, height (or length depending on age), and body weight (using a certified weight scale) at clinic visits.

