4.3 Demographics and Baseline Characteristics, Prior or Concomitant Medications

Demographics, baseline and disease characteristics

The following demographics, baseline and disease characteristics, medical and surgical history will be summarized using descriptive statistics in the FAS.

Demographic, baseline, and disease characteristics

- Age in years as quantitative variable and Age in years as categorical variables (Age group 1: 0 to <10, 10 to <18; Age group 2: 0 to <2, 2 to <12, 12 to <18) based on actual age.
- Age group (0 to <10, 10 to <18) from IWRS for randomization
- Gender (Male, Female)
- Race (American Indian or Alaska Native, Asian, Black or African American, Native Hawaiian or Other Pacific, Islander, White, Other, Not reported)
- Race group (White, Non-White (including race as not reported))
- Ethnicity (Hispanic or Latino, Not Hispanic or Latino, Not reported)
- Ethnicity group (Hispanic or Latino (including ethnicity as not reported), Not Hispanic or Latino)
- Country and region ([Appendix 4](#))
- Use of ursodeoxycholic acid (UDCA)
- Use of anti-pruritus medication
- Baseline values: height (or length depending on age), weight as quantitative and categorical (≤ 10 and > 10 kg) variable, body mass index (BMI), Z-score (height, weight, and BMI), pruritus score (i.e., AM, PM, average AM and PM scratching score from ObsRO), serum bile acid as quantitative and categorical (\geq median and $<$ median based on overall randomization population) variable, estimated glomerular filtration rate (eGFR), ALT, AST, gamma-glutamyl transferase (GGT), total bilirubin, direct bilirubin as quantitative and categorical (> 3 and ≤ 3 mg/dL), alkaline phosphatase (ALP), INR, cholesterol, triglycerides, vitamin A, vitamin E, and 25-hydroxy vitamin D.
- Disease characteristics include
 - Genetic testing results for ALGS if performed at screening (e.g., mutation in *JAG1* vs *NOTCH2*; per protocol, testing is only performed at screening if not available in the patient's medical record), years since ALGS diagnosis
 - Child-Pugh classification (mild (Class A), moderate (Class B), or severe hepatic impairment (Class C)), and hepatic impairment classification (no impairment, mild, moderate, or severe) per NCI Organ Dysfunction Working Group [6]. Details of the classification are described in [Appendix 9](#).

eGFR will be calculated based on the modified/bedside Schwartz equation. The values of eGFR will be provided by the central laboratory vendor.

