4.6.4 Other Secondary Endpoints

For all secondary endpoints, all data collected through the end of the study following an ICE due to premature discontinuation of study treatment prior to Week 24 (i.e., treatment policy strategy), will be included while excluding data following ICEs of biliary diversion surgery or liver transplant (i.e., hypothetical strategy).

The change in secondary endpoints such as serum bile acids, ALT, AST, gamma-glutamyl transferase, direct bilirubin, total bilirubin, total cholesterol, PRO and ObsRO sleep parameters will be summarized by visit using descriptive statistics.

In addition to evaluate vital signs (height and weight) in the safety analysis, growth data (height/length for age, weight for age, and BMI for age) will be considered as an exploratory efficacy endpoint. Growth data will be calculated using the software or methods from the Centers for Disease Control and Prevention (CDC) website [12] for patients with age ≥ 2 years old and from the World Health Organization (WHO) website [13] for patients with age < 2 years old.

Change from baseline in growth (i.e., height [cm], weight [kg], BMI [kg/m²] and corresponding linear growth compared to a standard growth curve [Z-score, SD from P50 standard growth curve], calculated by using the software or methods from the CDC website for patients with age \geq 2 years old and from the WHO website for patients with age $<$ 2 years old) will be summarized by visit using descriptive statistics.

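### SAP 4.8.2.2 subtracts 0.7 cm from every length with no age limit, and 4.6.4 does not exempt the WHO length-for-age and BMI-for-age z-scores of children under 2 years

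*SAP*

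**What the plan says.** Who is measured by length is left to age. Protocol Table 1 (footnote h) lists "height (or length depending on age), and body weight" among the vital signs, and Protocol 10.2.7 repeats this. Neither gives the age at which length gives way to standing height.

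SAP 4.8.2.2 (Vital Signs) summarises "height (or length depending on age), body weight (using a certified weight scale), and BMI" and then gives one rule: "If height is collected as length, it will be converted as following", followed by height = length − 0.7 cm. No age condition is attached and no analysis is exempted. Table 9 of the SAP (derived variables) has no entry for height, BMI or any growth z-score, so this is the SAP's only derivation of height from length.

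SAP 4.6.4 then says that "growth data (height/length for age, weight for age, and BMI for age) will be considered as an exploratory efficacy endpoint". Children of 2 years and over are scored with CDC software or methods. For those under 2 the calculation comes "from the World Health Organization (WHO) website [13] for patients with age" below 2 years. The same section summarises change in height in cm, in BMI in kg/m² and in the corresponding z-scores. SAP 4.6.4.1 adds an MMRM for change in growth. SAP 4.3 tabulates baseline "Z-score (height, weight, and BMI") and plans an age group of 0 to under 2 years, so children in the affected range are expected.

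**The concern.** By prescribing a 0.7 cm correction, the SAP accepts that length and standing height differ systematically. By naming the endpoint height/length for age, it accepts that some children are scored on length. Yet 4.8.2.2, applied as written, turns every length into a height, so no length is left to score. If the reference under 2 years is a length reference, each such child is entered 0.7 cm too short. The length-for-age z-score is then too low, and BMI is too high because its denominator is too small.

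What is at stake is the description of growth in the youngest children: the baseline z-scores that show how growth-impaired they are, and the z-score levels at each visit. SAP Appendix 1 says growth was added because these patients have impaired growth, so a downward shift in the baseline level bears on the feature the endpoint was added to study.

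**Working it through.** The plan gives no growth figure to reproduce. The 0.7 cm is a fixed constant, so the check is what follows from applying it.

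**Inputs**
- Conversion constant: 0.7 cm (SAP 4.8.2.2).
- Reference: WHO under 2 years, CDC from 2 years (SAP 4.6.4).
- SD of length-for-age in the reference: not in the documents; assumed 2.0 to 3.5 cm.
- Length of a child measured by length: not in the documents; assumed 50 to 90 cm.
- BMI for illustration: 16 kg/m² (assumed).
- That the under-2 reference is length-based: not stated in the documents; inferred from the endpoint label.

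**Length-for-age z, level.** Shift = −0.7/SD.

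| Assumed SD (cm) | Shift in z |
|---|---|
| 2.0 | −0.35 |
| 2.5 | −0.28 |
| 3.0 | −0.23 |
| 3.5 | −0.20 |

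**BMI, level.** BMI is weight divided by length squared, so using length − 0.7 multiplies it by (L/(L − 0.7))².

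| Assumed length (cm) | Factor | BMI of 16 becomes |
|---|---|---|
| 50 | 1.029 | 16.46 |
| 60 | 1.024 | 16.38 |
| 75 | 1.019 | 16.30 |
| 90 | 1.016 | 16.25 |

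**Change from baseline, child measured by length throughout.**
- Height in cm: the 0.7 cm is in both values and cancels exactly.
- Length-for-age z: artefact = 0.7/SD at baseline − 0.7/SD at follow-up. If the assumed SD rises from 2.0 to 2.3 cm, this is 0.350 − 0.304 = +0.05. From 3.0 to 3.5 cm it is 0.233 − 0.200 = +0.03.
- BMI of 16: artefact = 16 × (factor at follow-up − factor at baseline). For 60 to 67 cm it is −0.04 kg/m². For 78 to 83 cm it is −0.02 kg/m².

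**Change from baseline, child who moves from length to standing height.** Take the SAP's own 0.7 cm as the gap. If the conversion were dropped for the earlier visit, a child of 85 cm length would stand at 84.3 cm with no real change. Height in cm would show a false loss of 0.7 cm, and BMI a false rise of (85/84.3)² − 1 = 1.7%. For these two raw measures the conversion does useful work.

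**The case against.** The strongest reply is that the rule sits among the safety vital signs, while the z-scores are defined in 4.6.4, which never says that converted height feeds them. The WHO software could simply be given raw length, and the label height/length for age can be read that way. It is true that the SAP does not state the link. But 4.8.2.2 is the only derivation available, 4.6.4 lists height in cm with its corresponding z-score, and BMI appears beside the conversion rule. A programmer following the SAP literally would use the converted value. The size of the shift must therefore be stated as conditional, but the text does need correcting.

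It also stands that neither document says the WHO reference under 2 years is based on length, and that the SDs and lengths used here are assumed.

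A reader might go further and infer that the rule produces false catch-up growth: a child measured by length at baseline and standing after the second birthday would appear to gain in z. The documents do not support that as a signed bias. Section 4.6.4 changes the reference from WHO to CDC at age 2, so a change in z across that birthday also contains a change of standard, and its net direction cannot be read from the 0.7 cm alone. The number of such children is not given. The rule is the same in both arms, and the MMRM compares arms, so there is no systematic advantage to either.

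A reader might also infer that the conversion should be dropped altogether under 2 years. That does not hold for height in cm or BMI in kg/m², where dropping it would create the false loss and false rise shown above.

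**Conclusion.** The point holds as a minor defect in a stated rule. Applied as written, 4.8.2.2 leaves no length for the under-2 z-scores that 4.6.4 calls for. If the converted value enters a length-based reference, length-for-age z is about 0.20 to 0.35 too low and the BMI entering BMI-for-age about 1.6% to 2.9% too high. This rests on the assumed SDs and lengths and on the length basis implied by the endpoint label.

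The effect is mainly on baseline and by-visit z-score levels under 2 years. For children measured by length throughout, the residual in change is about +0.03 to +0.05 z. Both arms are treated alike, growth is exploratory, and the primary and key secondary analyses are not affected. The number of children under 2 is not stated, so the effect on overall summaries cannot be sized.

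**What to change.** In SAP 4.8.2.2 and 4.6.4:

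1. State that measured length, unconverted, is used for WHO length-for-age and BMI-for-age z-scores under 2 years.
2. State that length − 0.7 cm is used for z-scores only when the child is 2 years or older and length was recorded.
3. Keep the conversion for height in cm and BMI in kg/m², so that change from baseline stays on one scale for a child who moves from length to standing height.
4. Flag children who cross age 2 during the study, because the reference also changes from WHO to CDC. Say whether the reference is chosen by age at the visit; Table 9 defines age only at randomization.

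The cost is a few sentences in the SAP, one condition in the z-score derivation and one flag. No new data are needed beyond a record of whether each value was a length or a standing height, which the existing conversion already requires.

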4.9 Other Analyses

4.9.1 Pharmacokinetics (PK) Analyses

PK analysis will be specified in a separate PK SAP.

4.9.2 Blinded Analysis

4.9.2.1 Pruritus Responder Definitions

Blinded analyses of the Albireo ObsRO (or PRO) eDiary data will be performed when approximately 85% or more of the planned sample size has completed the Week 24 (or Week 12) visit. The blinded analysis will be used to estimate a threshold of clinically meaningful change (i.e., responder definition) in the Albireo ObsRO scratching score (or PRO itching score). The analysis will be performed by a group from IQVIA, independent from both the study team and Albireo. Blinded data will be used for this analysis; data will be collapsed across treatment groups.

The analyses will include distribution- and anchor-based analyses to examine a responder definition for the Albireo ObsRO scratching score (or PRO itching score). Distribution-based analyses will include calculation of the SD and standard error of measurement for the baseline

Albireo ObsRO scratching score (or PRO itching score). Anchor-based analyses will involve examining the degree of change on the Albireo ObsRO scratching score (or PRO itching score) from baseline to Week 24 (or Week12) for patients who experience change in pruritus according to PGIC and symptom items. This will be described in the PAP.

5 Supporting Documentation

5.1 Appendix 1 Changes to Protocol-Planned Analyses

This section summarizes major statistical changes in the protocol amendment(s).

Table 8 - Major statistical changes in protocol amendment(s)

Amendment Number	Approval Date	Changes	Rationale
V2.0	28Aug2020	Definition of the PP analysis set is changed for patients without major protocol violation to patient without important protocol violation. Additional criteria are added.	Correct the definition of the PP analysis set.
		The covariate of baseline conjugated bilirubin in MMRM is changed to direct bilirubin.	Align with the routine laboratory parameters collected during the study
		The contrast statement for month 6 (weeks 21 to 24) to assess treatment effect is changed to the difference of the least square mean estimate.	The difference of the least square mean estimate will produce the same result as the contrast statement for the primary endpoint at Month 6 and provide data for the preceding visits.
		Add growth as an exploratory efficacy endpoint	Patients with ALGS have impaired growth. To evaluate the effect of odevixibat on growth.

5.2 Appendix 2 Derived Variables

The table below provides the list of derived variables for demographic and baseline characteristics, various duration derivations, drug compliance, baseline derivations and other important protocol derivations applicable for this study.

Table 9 – Derivation rules for the derived variable

Variables	Formula
Demographic and Baseline characteristics	
Age (in years)	For patients not from site CCI : Age is calculated based on date of birth and date of randomization. It will be derived by SAS YRDIF function: yrdif (Date of birth, Date of Randomization, "ACT/ACT") For patients from site CCI : Only year of birth was collected, and January 1 was imputed in the eDC system. For analysis purpose, age is calculated based on collected age months and age years on the CRF.
Derivation of Duration	
Study day at any visit	Date of interest – Date of first dose of study drug. One day is added if this difference is ≥ 0
Extent of Exposure	
Duration of treatment exposure (days)	Date of last study drug intake – Date of first study drug intake + 1
Average Daily dose (ug/kg/day)	Sum of (number of capsules taken per day * dose strength of the capsules per weight category * dose duration under this dose amount/weight) / (Date of last study drug intake – Date of first study drug intake + 1)
Overall Study Drug Compliance	
Compliance	$100 \times \text{sum of (number of capsules actually taken)} / \text{sum of (number of capsules planned to be taken per day * dose duration under this planned dose amount)}$
Last participant date	Last contact date or date of death which occurred first
Derivation for Efficacy Parameters	
Baseline (general)	The baseline value of a parameter is defined as the last assessment of that parameter prior to the first intake of study treatment, except as indicated below
Baseline for serum bile acid	The baseline will be calculated as the average of the last 2 values prior to the first dose (central laboratory results will be used over local laboratory results). If only one non-missing value is available, it will be used as baseline.
Average serum bile acid of Week 20 and Week 24	The average of values that identified from analysis window at Week 20 and Week 24.
Daily score for ObsRO scratching (or PRO itching) severity	The daily score is calculated by averaging the PM score and the next day AM score. The daily score is calculated if at least the PM score or the next day AM score is collected.

Variables	Formula
Weekly AM (or PM) score for ObsRO scratching (or PRO itching) severity	The weekly AM (or PM) score is calculated by averaging the AM (or PM) scores in a week. Each week, at least 4 of 7 AM (or PM) assessments need to be collected to calculate the weekly AM (or PM) score (i.e., 50% rule). If these minimum assessments are not available, the weekly AM (or PM) score is considered missing
Weekly average score for ObsRO scratching (or PRO itching) severity	The weekly average AM and PM score is calculated by averaging of (the average of AM scores, the average of PM scores) in a week. Each week, at least 7 of 14 AM or PM assessments need to be collected to calculate the weekly average AM and PM score (i.e., 50% rule) regardless how many AM assessments or how many PM assessments are collected respectively. If these minimum assessments are not available, the weekly average AM and PM score is considered missing.
Baseline score for ObsRO scratching (or PRO itching) severity (general)	The baseline AM (or PM, or average AM and PM) score is calculated by averaging the two-baseline weekly AM (or PM, or average AM and PM) scores in the 14 days preceding start of treatment. Baseline score will be unrounded. Baseline values can only be calculated if both weeks can be calculated.
Baseline score for ObsRO scratching (or PRO itching) severity (sensitivity analysis)	The baseline AM (or PM, or average AM and PM) score is calculated by averaging the four-baseline weekly AM (or PM, or average AM and PM) scores in the 28 days preceding start of treatment. Baseline score will be unrounded. Baseline values can only be calculated if 2 or more weeks score can be calculated.
Monthly average score for ObsRO scratching or (PRO itching) severity	The post-baseline monthly (28 days) AM (or PM, or average AM and PM) score is calculated by averaging 4 weekly scores within the 4-week interval. The monthly AM (or PM, or average AM and PM) score can only be calculated if at least 3 of 4 weekly scores within the 4-week interval can be calculated.
Baseline for worst weekly score for ObsRO scratching (or PRO itching) severity	The baseline for worst weekly score is calculated by taking the worst daily score as the maximum of the PM score and the next day AM score in the 14 days preceding start of treatment, then calculating the worst weekly score by taking the average of the worst daily scores in a week (7 days), and finally calculating the worst weekly score for baseline as the maximum of the worst weekly scores within the 2-week interval. At least one of the PM score or the next day AM score need to be collected to calculate the worst daily score. At least 4 of 7 worst daily scores within the week are needed to calculate the worst weekly score. The worst weekly score for baseline is calculated if at least one worst weekly score within the 2-week interval can be calculated.
Worst weekly score for a month for ObsRO scratching (or PRO itching) severity	The worst weekly score for a month (28 days) is calculated by taking the worst daily score as the maximum of the PM score and the next day AM score, then calculating the worst weekly score by taking the average of the worst daily scores in a week (7 days), and finally calculating the worst weekly score for a month as the maximum of the worst weekly scores within the 4-week interval. At least one of the PM score or the next day AM score need to be collected to calculate the worst daily score. At least 4 of 7 worst daily scores within the week are needed to calculate the worst weekly score. The worst weekly score for a given month is calculated if at least one worst weekly score within the 4-week interval can be calculated. The worst weekly score for a month is calculated for each month of post-baseline

Variables	Formula
Change from baseline for ObsRO scratching or (PRO itching) severity score	The daily, weekly, monthly AM (or PM, or average AM and PM) score change from baseline is calculated by subtracting the baseline AM (or PM, or average AM and PM) score from the daily, weekly, monthly AM (or PM, or average AM and PM) score
Change from baseline for worst weekly score for a month for ObsRO scratching (or PRO itching) severity	Change from baseline in the worst weekly score for a month is calculated by subtracting the worst baseline score from the worst weekly score for a month
Average Month 4 to 6 and change from baseline	Average of all available monthly scores through Month 4 to 6. Change from baseline through Month 4 to 6 is calculated by subtracting the baseline score from the average of monthly scores through Month 4 to 6.
Baseline and monthly score for sleep parameters (such as difficulty of falling asleep and staying asleep, tiredness, and the number of awakening)	For patient- and observer- reported outcome scores of sleep parameters, the same approach above will be used as for scratching (or itching) severity score by AM and PM respectively since there is just 1 rating per day.
PRO and ObsRO Assessment Scores for psychometric analyses	Please refer to psychometric analysis plan
Derivation for Safety Parameters	
AE duration (days)	AE end date – AE start date +1
TEAE	An AE (classified by preferred term) that occurs during the Treatment Period will be considered a TEAE if it has a start date on or after the first dose date of study drug, or it has a start date before the date of the first dose date of study drug, but worsened in severity on or after the date of the first dose date of study drug

